Nivolumab Administration	X		X			X			Nivolumab will be administered every 3 weeks for the first 2 cycles (4 doses) and then every 4 weeks for Cycle 3 and beyond. See Section 7.1 for nivolumab dose administration.		
Ipilimumab Administration	X		X						Ipilimumab will be administered every 3 weeks on Cycles 1 and 2 (4 doses) ONLY. See Section 7.1 for ipilimumab dose administration.		

Date: 17-May-2024

Approved v 8.0 930120018 9.0

Abbreviations: AFP, alpha fetoprotein; BICR, blinded independent central review; C, Cycle; CT, computed tomography; d, days; D, day; ECG, electrocardiogram; ECOG, Eastern Cooperative Oncology Group; EDC, Electronic Data Capture; EOT, end of treatment; HCC, hepatocellular carcinoma; hCG, human chorionic gonadotropin; IRT, Interactive Response Technologies; MRI, magnetic resonance imaging; PK, pharmacokinetic(s); QXW, every X weeks; SAE, serious adverse event; T3, triiodothyronine; T4, thyroxine; TSH, thyroid stimulating hormone; WOCBP, women of childbearing potential.

- a For participants who complete all scheduled cycles of therapy, the EOT visit will be the same visit as the last scheduled and completed on-treatment visit and the start of the Week 1 Clinical/Safety Follow-up visit.
- b For participants who do not complete all scheduled cycles of therapy, the EOT visit will be the next visit following the last study dose. If the EOT visit occurs 30 days or more after receipt of the last dose, then the EOT visit and Follow-up 1 visit can be completed at the same time.
- c If multiple procedures are required at a single timepoint, safety assessments (ECGs, vital signs, and pulse oximetry) are a higher priority than PK/immunogenicity sampling.

Protocol Amendment No.: 07

 Table 2-7:
 Safety Follow-up Procedural Outline

	FU 1	FU 3	Response Follow-up	Notes
Procedure	30 Days (± 7 Days)	100 Days (± 7 Days)	(Q12W)	
Safety Assessments				
Concomitant Medications	X	X		
ECOG Performance Status	X	X		Appendix 5
Physical Examination	X	X		
Vital Signs/Oxygen Saturation and Weight	X	X		Including weight, body temperature, respiratory rate, pulse oximetry, seated BP, and heart rate.
Laboratory Tests				
Hematology and Serum Chemistry	X	X		See Section 9.1.4  Only applicable for Part 1C: For HCC participants: AFP
Pregnancy testing (WOCBP)	X	X		
Pharmacokinetic Assessment				
PK / Immunogenicity Sampling	S	ils		

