### 5.1.3 Treatment Period

Physical examinations, vital sign or pulse oximetry measurements, 12-lead ECGs, and clinical laboratory evaluations will be performed at selected times throughout the study (see Section 2).

Participants will be closely monitored for AEs throughout the study. Blood samples will be collected at selected times for PK and pharmacodynamic analysis as per Section 9.8,

In Part 1, stool will be collected during screening, on treatment, and at progression to evaluate pharmacodynamic effect in relation to the gut microbiota (per Section 9.8,

In Part 2, stool will be collected during screening only (per Section 9.8,

All participants will be treated for up to 3 calendar years from first dose or until disease progression, intolerance to treatment, meeting discontinuation criteria, or withdrawal of consent.

Participants enrolled in the safety evaluation lead-in period (Part 1A), will start with a 4-week DLT evaluation following the first dose (corresponding to the first cycle of the treatment period). A sentinel participant approach will be used with a 5-day interval between the treatment initiation of the first participant and the treatment of subsequent participants at each dose level that will be

tested in Part 1A. Participants enrolled in the dose-finding (Part 1B), in the triplet safety assessment (Part 1C), and in Part 2 of the study will start their treatment period at the dose regimen according to their assigned cohort, respectively. Additional cohorts in Part 1 may start with a safety lead-in (4-week DLT evaluation) as previously described.

Study visits and samples collections will vary based on cohort assignment as per Sections 9.5 and 9.8.

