## 9.5 Pharmacokinetics and Immunogenicity Assessments

Following the final analysis, PK and IMG samples will no longer be collected.

Pharmacokinetic (PK) and immunogenicity (IMG) assessment data for BMS-986253, nivolumab, and ipilimumab will be collected from study participants assigned to the study at the time points indicated

All time points are relative to the start of the first drug administration on that day. All on-treatment time points are intended to align with days on which study drug is administered; if dosing occurs on a different day, the PK and IMG sampling should be adjusted accordingly. If it is known that a dose is going to be delayed, then the predose sample should be collected just prior to the delayed dose. However, if a predose sample is collected but the dose is subsequently delayed, an additional predose sample should not be collected. All predose samples should be taken within 30 minutes before the start of any dose infusion. End of infusion (EOI) samples should be taken immediately prior to completion of the infusion, preferably within 2 minutes. Blood samples should be drawn from a site other than the infusion site (ie, contralateral arm) on days of infusion.

Pharmacokinetics of BMS-986253 will be derived, if feasible, from serum concentration versus time data following administration of BMS-986253. PK parameters that will be assessed are shown below:

Table 9.5-1: Pharmacokinetic Parameters

Cmax	Maximum observed serum concentration
Tmax	Time of maximum observed serum concentration
AUC(0-T)	Area under the serum concentration-time curve from time zero to time of last quantifiable concentration; may be calculated if concentrations are not quantifiable up to TAU across a treatment group
AUC(TAU)	Area under the serum concentration-time curve in 1 dosing interval
Ctau	Observed serum concentration at the end of a dosing interval
Ctrough	Trough observed serum concentrations (this includes pre-dose concentrations [C0] and Ctau)

[figure not shown]
Table 9.5-2: Pharmacokinetic Parameters that May be Assessed Following the Administration of BMS-986253

CLT	Total body clearance
Css-avg	Average serum concentration over a dosing interval (AUC[TAU]/tau) at steady state
AI	Ratio of an exposure measure at steady state to that after the first dose (exposure measure includes AUC[TAU] and Cmax)

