# 10.2 Populations for Analyses

Population	Description	
Enrolled/Randomized	All participants who have signed informed consent and are registered into the IRT	
Treated	All participants who received at least 1 dose of study treatment	
Efficacy	All participants who take at least 1 dose of their planned full combination treatment.	
Response-evaluable	All treated participants with measurable disease at baseline and one of the following: (1) at least 1 post-baseline tumor assessment, (2) clinical progression, or (3) death	
Pharmacokinetic	All treated participants who have evaluable concentration-time data	

Population	Description
Immunogenicity	All treated participants who have baseline and at least one post baseline immunogenicity assessment
Biomarker	All treated participants with available biomarker data

Abbreviation: IRT, Interactive Response Technologies.

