# 10.3.4 Immunogenicity Analyses

presented in a separate report.

Endpoint	Statistical Analysis Methods	
Incidence of ADA to BMS-986253, nivolumab, or ipilimumab administrated in combination	Frequency distribution of baseline ADA-positive participants and ADA-positive	
Baseline ADA-positive participant is defined as a participant who has an ADA detected sample at baseline. ADA-positive participant is a participant with at least 1 ADA-positive sample relative to baseline after initiation of the treatment	participants after initiation of the treatment; summary of ADA peak titer, ADA onset and duration, summary of select AEs by ADA status, summary of BOR by ADA status	

Abbreviation: ADA, anti-drug antibody; AE, adverse event; BOR, best overall response.

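### Best overall response and select AEs are tabulated by an ever-positive ADA status with no time window, so the descriptive response table can show a spurious association in favour of ADA-positive participants

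*Combined protocol and SAP*

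**What the plan says.** Section 10.3.4 defines status without a time limit: "ADA-positive participant is a participant with at least 1 ADA-positive sample relative to baseline after initiation of the treatment". The same row plans a "summary of select AEs by ADA status, summary of BOR by ADA status". It also plans a "summary of ADA peak titer, ADA onset and duration", but does not link onset to either of the two tables by status.

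Section 10.2 sets a low entry bar for the immunogenicity population: "All treated participants who have baseline and at least one post baseline immunogenicity assessment". No minimum number of samples or length of follow-up is required.

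Three other places determine how long a participant can be sampled:
- Section 5.1.3: "All participants will be treated for up to 3 calendar years from first dose or until disease progression", or until another listed stopping reason.
- Section 9.5: "All on-treatment time points are intended to align with days on which study drug is administered". The only stop to collection in the visible text is this: "Following the final analysis, PK and IMG samples will no longer be collected".
- Table 2-7 lists immunogenicity sampling in safety follow-up, where visits fall at Days 30 and 100 after the last dose.

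Table 10.3.1-2 closes the window for best overall response in Part 2 at first progression or subsequent therapy. ADA status has no matching window.

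**The concern.** Ever-positive status accumulates over follow-up, and the length of follow-up depends partly on outcome. Someone who progresses early leaves treatment and has few chances to test positive. A responder who stays on treatment may have many. A response first seen on the Week 8 scan and confirmed at Week 16 is already settled, yet a first positive sample months later moves that participant into the ADA-positive responders. Status is then partly a consequence of response, which is the familiar immortal-time problem.

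The artefact pushes responders towards the ADA-positive group. If antibodies really do reduce efficacy, the table could hide it. If they do nothing, the table could make them look favourable. For adverse events the difficulty is one of order: an event in the first cycle can be tabulated under an ADA that was first detected much later.

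**Working it through.** The plan states no figure for this analysis, so there is none to reproduce. The check asks how large a gap arises when ADA is truly unrelated to response.

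**Inputs.** From the documents: a response rate of 30%, between the 29% and 31% cited in Section 5.4.8 for ipilimumab plus anti-PD-(L)1 after anti-PD-(L)1 failure. Assumed, because the documents do not give them: ADA rate, number and timing of samples, and time on treatment by response.

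**Step 1: simple formula.** Let h be the chance of a first positive result at each sample and k the number of samples. Then P(ever positive) = 1 − (1 − h)^k. With h = 3%:
- 12 samples per responder: 1 − 0.97^12 = 30.6%.
- 4 samples per non-responder: 1 − 0.97^4 = 11.5%.
- ORR in ADA-positive = 0.30 × 0.306 / (0.30 × 0.306 + 0.70 × 0.115) = 53%.
- ORR in ADA-negative = 0.30 × 0.694 / (0.30 × 0.694 + 0.70 × 0.885) = 25%.

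The spurious odds ratio is about 3.4. With 6 against 4 samples it is 1.55 (38% against 29%). With 4 against 4 it is 1.00 (30% against 30%). Over h from 1% to 10% and sampling from 6 against 4 to 15 against 4, it runs from 1.5 to 7.4. Unequal sampling is therefore what creates the gap.

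**Step 2: simulation in time.** Exponential time on study is truncated to 1 to 24 months. ADA onset is exponential at 1%, 2% or 4% per month, independent of response. A participant is positive if onset falls on or before the last sample. Unless stated, samples are at months 1, 2, 3 and then every 3 months to month 24.

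| Assumption (median months, responders vs non-responders) | ORR ADA-positive | ORR ADA-negative | Gap (points) |
|---|---|---|---|
| 14 vs 3, sampling stops at discontinuation | 60 / 58 / 56% | 28 / 27 / 24% | about 32 |
| 14 vs 3, plus a sample at about Day 100 after treatment | 48 / 47 / 44% | 28 / 26 / 23% | about 20 |
| 8 vs 3, plus that sample | 42 / 41 / 39% | 29 / 28 / 26% | about 13 |
| 6 vs 4, plus that sample | – | – | 5 to 6 |
| 14 vs 3, on-treatment samples at months 1 to 3 only, no follow-up sample | about 36% | about 30% | about 6 |
| 14 vs 3, ADA onset only in first 3 months, plus Day-100 sample | 30% | 30% | 0 |
| 14 vs 3, one sample at month 1 only | – | – | 0 |

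A separate simulation used a 3% or 6% chance per sample. With sampling confined to Weeks 2 and 4, with or without two follow-up samples, the gap was only 1 to 2 points.

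**Step 3: does a landmark remove it?** With the first-row assumptions, status fixed at month 2 among those still on treatment and sampled gives ORR 38 to 39% in ADA-positive against 38% in ADA-negative. In the per-sample simulation, a Week 12 landmark gives 46% against 46%, or 42% against 42%, depending on the durations assumed. The rates exceed 30% because early discontinuers leave both groups; the gap is gone.

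**Step 4: adverse events.** No bias was computed. Longer treatment raises both the number of events and the number of samples, while stopping early for an event cuts the number of samples. The direction is not fixed.

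**The case against.** The strongest reply is that the governing detail is out of sight. Section 10.3 calls itself a summary and defers to a SAP, and Appendix 13 records that the wording on ADA status was brought in at Amendment 06 to match an immunogenicity analysis plan. Neither plan is among the documents, and either could set a window. The sampling tables of Section 9.5 are redacted as well. This limits certainty about the practical effect. It does not undo the definition in Section 10.3.4, which is an explicit any-time rule.

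A reader might infer that responders here do give more samples and do turn positive more often. The visible text makes this likely but does not establish it; if sampling is early and fixed, the gap is near zero. A reader might also take the 32-point gap as the expected error. That figure ignores the follow-up sampling in Table 2-7 and is close to a worst case.

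Two further points stand. The tables are descriptive, with no test, model or decision rule, and the visible Part 1 endpoint is only the incidence of ADA to BMS-986253. ADA onset and duration are also summarised, so a reader can see whether positivity tends to be early or late. That helps interpretation but does not correct the response table.

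**Conclusion.** The point holds as a minor improvement. An ever-positive status with no window, set against treatment that ends at progression, lets the response table show an association where none exists, in the direction that favours ADA-positive participants.

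The size is unknown. Under a 30% response rate and ADA independent of response, it ranges from about 0 to about 20 points when follow-up samples are taken, and reaches about 32 only if sampling stops at discontinuation. It depends on the assumed schedule, the onset pattern and the difference in treatment duration.

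The documents do not support reading this as a threat to the trial's efficacy conclusions: the primary ORR comparison and the main safety tables do not use ADA status. Nor do they support a claim about the direction of any bias in the adverse event table.

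**What to change.** In the SAP:
1. Keep ever-positive status for the incidence table.
2. Add a best overall response table by ADA status at a landmark, meaning an already scheduled early sample at or before about the first on-study scan (Week 8), among participants still on treatment and sampled at that time.
3. For select adverse events, also show events by whether they began before, or on or after, the first ADA-positive date, with exposure-adjusted rates and time before that date counted as ADA-negative.
4. If the ever-positive response table is kept alongside, add a caveat and the number of post-baseline samples by ADA status.

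If the redacted schedule is in fact early and fixed, or the immunogenicity plan already sets a window, one sentence saying so would settle the matter.

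The cost is SAP wording and table programming. No new samples are intended, provided the schedule contains a suitable early sample, which cannot be checked here. The downsides are a smaller ADA-positive group, the loss of participants who are off treatment or unsampled at the landmark, and late-onset ADA counted as negative in that table. The last is the reason for keeping the ever-positive table beside it.

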# 10.3.5 Biomarker Analyses

Endpoint	Statistical Analysis Methods
Summary measures of absolute values of serum IL-8, and change (or percent change) from baseline in serum IL-8	Summary statistics by planned study day and cohort; Plots of the time course of biomarkers, geometric mean of the ratio of post-baseline IL-8 and corresponding CI.

[figure not shown]
Abbreviations: CI, confidence interval; IL-8, interleukin-8.

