# 4 OBJECTIVES AND ENDPOINTS

Table 4-1: Objectives and Endpoints - Part 1

Objectives	Endpoints
Primary	
To characterize safety, tolerability, and DLTs, and to determine the RP2D of BMS-986253 administered in combination with nivolumab, or in combination with nivolumab and ipilimumab in participants with advanced solid tumors.	Incidence of AEs, SAEs, AEs meeting protocol- defined DLT criteria, and AEs leading to discontinuation, death, and laboratory abnormalities.
Secondary	

 
To evaluate the preliminary efficacy of BMS-986253 in combination with nivolumab in participants with advanced solid tumors using RECIST v1.1.
 
To characterize the PK and immunogenicity of BMS-986253 when administered in combination with nivolumab, or in combination with nivolumab and ipilimumab in participants with advanced solid tumors.
 
To assess serum IL-8 levels at baseline (ie, screening) and changes in IL-8 levels on treatment.
 
	
 
ORR and DOR per RECIST v1.1 per investigator.
 
Summary measures of PK parameters and incidence of ADA to BMS-986253.
 
Summary measures of IL-8 and change (or percent change) from baseline in IL-8 on treatment.
 

Abbreviations: ADA, anti-drug antibody; AE, adverse event; DLT, dose-limiting toxicity; DOR, duration of response; EOT, end of treatment; ORR, objective response rate; PK, pharmacokinetic(s);

Protocol Amendment No.: 07

RECIST, Response

Evaluation Criteria in Solid Tumors; RP2D, recommended Phase 2 dose; SAE, serious adverse event.

[figure not shown]
Table 4-2: Objectives and Endpoints - Part 2

	Objectives	Endpoints
Pri	imary	
•	To compare the ORR of BMS-986253 plus nivolumab plus ipilimumab with placebo plus nivolumab and ipilimumab using RECIST v1.1.	ORR based on BICR assessments per RECIST v1.1 in all randomized participants.
Sec	condary	
•	To estimate PFS of BMS-986253 plus nivolumab plus ipilimumab and placebo plus nivolumab and ipilimumab in participants with advanced melanoma using RECIST v1.1 (regardless of baseline serum IL-8 levels).	mPFS and PFS hazard ratio based on BICI assessments per RECIST v1.1.
•	To compare the safety of BMS-986253 plus nivolumab plus ipilimumab with placebo plus nivolumab plus ipilimumab in participants with advanced melanoma.	discontinuation, death, and laborator

Protocol Amendment No.: 07

Date: 17-May-2024 68

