# 5.4.1 Rationale for Targeting IL-8 in Cancer

IL-8 (CXCL8) is a chemokine whose main physiologic function is the attraction of a polymorphonuclear inflammatory leukocyte infiltrate acting on CXCR1/2. Recently, it has been found that tumors frequently produce IL-8, which exerts different pro-tumoral functions, including

Protocol Amendment No.: 07

angiogenesis, provide growth factors and survival signaling for CSCs as well as the attraction of immunosuppressive myeloid cells endowed with the ability to dampen anti-tumor immunity. In the tumor, IL-8 is mainly produced by cancer cells themselves. IL-8 serum concentration has been shown to correlate with cumulative tumor size, stage, and prognosis in numerous cancer types.  Because of a short concentrations closely follow in time the changes occurring in IL-8-producing cells. Recent data strongly support a correlation between serum IL-8 levels and tumor burden as well as clinical stage in patients with melanoma, RCC, NSCLC, and HCC.  In fact, patients with higher serum IL-8 levels had worse overall survival (OS). Because of the roles that IL-8 plays in favoring tumor progression through several mechanism such as modulating chemotaxis, resistance to therapy, angiogenesis, and metastasis, therapeutic strategies aiming to interfere with IL-8 has the potential to alleviate these functions, thereby diminishing the risk of (further) metastatic spread and recurrent disease in these patients. Anti-IL-8 neutralizing antibody (HuMax-IL-8) was shown to decrease IL-8-induced neutrophil activation and migration in vitro resulting in beneficial anti-inflammatory responses in patients with palmoplantar pustulosis which also provided support to test this antibody in cancer patients.

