### 5.4.2 Rationale for the Combination of BMS-986253 and Nivolumab

[figure not shown]
Recent reports have shown that changes in serum IL-8 levels accurately correlate with tumor burden changes in metastatic melanoma and NSCLC patients during treatment with anti-PD-(L)1 mAbs and in metastatic melanoma patients during treatment with anti-PD-(L)1 plus anti-CTLA-4 mAbs.  In fact, increased expression of IL-8 by cancer cells could contribute to immuno-resistance by promoting the recruitment of immunosuppressive myeloid derived cells.  These cells are well known to dampen the cytotoxic ability of T-Cells by various mechanism.  Preliminary data, from multiple trials with nivolumab, show that a high level of serum IL-8 at baseline that persists or increases throughout therapy correlates with decreased response and survival in melanoma, NSCLC and RCC (see BMS-986253 IB). In the preclinical models, the combination of a PD-(L)1 inhibitor and an IL-8 axis inhibitor was better at reducing tumor growth than either agent given as monotherapy suggesting a specific immunosuppressive role for IL-8.  IL-8 produced in the tumor attracts MDSCs into the tumor microenvironment and these cells can in turn inhibit the immunological response to the tumor by T-lymphocytes; further confirming that IL-8 signaling is involved in tumor immunosuppression. 

Based on these data, the combination of nivolumab with BMS-986253 could demonstrate a synergetic anti-tumor activity. IL-8 serum levels may be used to guide choice of dose in pivotal efficacy trials of BMS-986253 in advanced cancer participants with resistance to anti-PD-L1 therapies.

[figure not shown]

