#### 8 DISCONTINUATION CRITERIA

## 8.1 Discontinuation from Study Treatment

Participants MUST discontinue IP for any of the following reasons:

- Documented disease progression as defined by RECIST v1.1 (Appendix 8) unless participants meet criteria for treatment beyond progression (Section 8.1.1).
- Clinical deterioration while receiving active study therapy that, in the opinion of the investigator, indicates that continued participation in the study is not in the best interest of the participant.
- Any drug-related AE occurring at any time that meets DLT criteria as outlined in Section 7.6.1 will require permanent discontinuation of the implicated study drug. Exceptions to permanent discontinuation are listed in Section 7.6.5.
- Participant's request to stop study treatment. Participants who request to discontinue study
  treatment will remain in the study and must continue to be followed for protocol-specified
  follow-up procedures. The only exception to this is when a participant specifically withdraws
  consent for any further contact with him/her or persons previously authorized by participant to
  provide this information.
- Any clinical AE, laboratory abnormality or intercurrent illness which, in the opinion of the investigator, indicates that continued participation in the study is not in the best interest of the participant.
- Termination of the study by BMS for reasons stated in Section 8.2.1.
- Loss of ability to freely provide consent through imprisonment or involuntarily incarceration
  for treatment of either a psychiatric or physical (eg, infectious disease) illness. (Note: Under
  specific circumstances and only in countries where local regulations permit, a participant who

has been imprisoned may be permitted to continue as a participant. Strict conditions apply and BMS approval is required.)

- Inability to comply with protocol.
- Discretion of the investigator.
- Pregnancy.
- Individual participants with confirmed complete response (CR), and all participants after final analysis results are available, will be given the option to discontinue any or all of the study therapies on a case by case basis after specific consultation and agreement between the investigator and BMS Medical Monitor in settings where benefit/risk justifies discontinuation.
- Any event that leads to delay in dosing, lasting > 8 weeks from the previous dose, requires discontinuation, with the exception of the following:

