#### 8.1.1 Treatment Beyond Progression

As described in Section 5.4.6, accumulating evidence indicates that a minority of participants with tumors treated with immunotherapy may derive clinical benefit despite initial evidence of disease progression. Participants will be permitted to continue treatment beyond initial RECIST v1.1-defined disease progression, as assessed by the investigator (see Appendix 8), as long as they meet the following criteria:

- Investigator-assessed clinical benefit, and no rapid disease progression.
- Continue to meet all other study protocol eligibility criteria.
- Tolerance of study treatment.
- Stable performance status.
- Treatment beyond progression will not delay an imminent intervention to prevent serious complications of disease progression (eg, CNS metastases).
- Participant provides written informed consent prior to receiving any additional nivolumab, ipilimumab, and BMS-986253 treatment, using an ICF describing any reasonably foreseeable risks or discomforts, or other alternative treatment options.

The assessment of clinical benefit should take into account whether the participant is clinically deteriorating and unlikely to receive further benefit from continued treatment. If the investigator feels that the participant continues to achieve clinical benefit by continuing treatment with the study treatments, the participant should remain on the trial and continue to receive monitoring according to the Schedule of Activities (see Section 2). All decisions to continue treatment beyond initial progression must be discussed with the BMS Medical Monitor, and an assessment of the risk/benefit of continuing with study therapy must be documented in the study records (see Appendix 2).

Participants must be re-consented with an ICF addendum or similar document to continue treatment beyond progression. Treatment beyond progression will require continued tumor assessments and scans should continue to be submitted to the imaging core laboratory.

Participants who continue study therapy beyond progression will continue to receive monitoring according to the on-treatment assessments in Section 2, and radiographic assessment per Section 9.4.1 and Section 2 to determine whether there has been continued disease progression or not.

Further progression is defined as an additional 10% increase in tumor burden with a minimum 5 mm absolute increase from time of initial progression of disease. This includes an increase in

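### The by-day serum IL-8 summary can show, or exaggerate, a late fall because progressors drop out of it, if on-drug IL-8 change still follows tumour change

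*Combined protocol and SAP*

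**What the plan says.** Table 4-1 (Section 4) lists a Part 1 secondary objective, "To assess serum IL-8 levels at baseline (ie, screening) and changes in IL-8 levels on treatment", with the endpoint "Summary measures of IL-8 and change (or percent change) from baseline in IL-8 on treatment". The visible analysis in Section 10.3.5 is "Summary statistics by planned study day and cohort; Plots of the time course of biomarkers, geometric mean of the ratio of post-baseline IL-8", with a confidence interval. The biomarker population in Section 10.2 is "All treated participants with available biomarker data", so the denominator on any day is whoever has a sample that day. No longitudinal model, fixed-cohort display or dropout rule for IL-8 is visible. Section 10.3 leaves missing-data procedures to the SAP in general terms.

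Three other parts of the protocol bear on who remains:

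- **IL-8 and tumour burden.** Section 5.4.1 cites "a correlation between serum IL-8 levels and tumor burden". Section 5.4.2 says that "changes in serum IL-8 levels accurately correlate with tumor burden changes in metastatic melanoma and NSCLC patients during treatment with anti-PD-(L)1 mAbs", and extends this to melanoma treated with anti-PD-(L)1 plus anti-CTLA-4. Section 9.8.1 adds that early IL-8 changes predict response and survival.
- **Leaving treatment.** Section 8.1 requires discontinuation for "Documented disease progression as defined by RECIST v1.1 (Appendix 8) unless participants meet criteria for treatment beyond progression". Section 8.1.1 gives the exception: "Participants will be permitted to continue treatment beyond initial RECIST v1.1-defined disease progression".
- **Timing.** Section 9.4.1 schedules scans every 8 weeks (± 7 days) up to week 48. The Protocol Summary says that biomarkers are also measured at progression.

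**The concern.** A mean taken over available samples at each visit describes a different set of people at each visit. If those who leave are those whose IL-8 rose, or fell least, the plotted curve moves down as they go, even when nobody's own IL-8 changes course. A reader would take this for deepening or durable suppression. Cohorts with different progression rates would also be compared on differently selected remainders.

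The stake is interpretive. Section 5.4.2 says that serum IL-8 may help guide dose choice in later pivotal trials, and Section 5.5.2 uses IL-8 suppression as one strand of the dose rationale. The endpoint is descriptive, and no IL-8 hypothesis test is shown.

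**Working it through.** The documents give no dropout rate, IL-8 variance or on-drug correlation, so there is no stated figure to reproduce. Every numerical input below is an assumption, apart from the 8-week scan interval and the 20% growth threshold for progression (Appendix 8).

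**Step 1: closed form.** Let a share p progress and leave, and let progressors' ratio to baseline be R times that of the rest. The full-cohort geometric mean is G × R^p and the observed one is G, so observed ÷ full = R^(−p).

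| p | R | R^(−p) |
|---|---|---|
| 0.3 | 1.25 | 0.94 |
| 0.5 | 1.5 | 0.82 |
| 0.7 | 3 | 0.46 |

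If progressors' IL-8 change is no different (R = 1), the factor is 1.

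**Step 2: exit at the scan.** Assume a log tumour slope with mean 0 and SD 0.2 per 8 weeks. Assume log IL-8 change with SD σ = 0.5 per 8 weeks and correlation ρ with tumour change. Participants leave after the scan that shows 20% growth, with the sample at that scan kept. Those still present at week t have a standardised slope below c = ln(1.2) ÷ (0.2k), where k is the number of 8-week intervals to the previous scan. Then

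observed ÷ true = exp[−ρ × σ × (t/8) × φ(c)/Φ(c)]

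- Week 8: nobody has yet left through a scheduled scan, so the factor is 1.00.
- Week 16: k = 1, c = 0.912, φ/Φ = 0.3215. At ρ = 0.6: exp(−0.6 × 0.5 × 2 × 0.3215) = 0.82. At ρ = 0.3: 0.91.
- Week 24: k = 2, c = 0.456, φ/Φ = 0.532. At ρ = 0.6: exp(−0.6 × 0.5 × 3 × 0.532) = 0.62. At ρ = 0.3: 0.79.
- ρ = 0: the exponent is 0, so the ratio does not drift at any visit.

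The factor multiplies whatever ratio the drug produces. With 80% suppression, 0.20 would read 0.12 at week 24 (0.20 × 0.62).

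A simulation of 400,000 participants on these inputs gave the same values at weeks 16 and 24. At week 48 it gave 0.30 (ρ = 0.6) and 0.55 (ρ = 0.3).

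**Step 3: sensitivity at ρ = 0.6, week 24 (simulated).**

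| Change to inputs | Observed ratio when the true ratio is 1.00 |
|---|---|
| 30% treated beyond progression | 0.69 |
| No sample at the progression scan | 0.58 |
| IL-8 change SD 0.2 instead of 0.5 | 0.83 |

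Without a progression sample, the loss already shows at week 8 (0.91).

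Absolute IL-8 values are also summarised, and these can drift even at ρ = 0. Losing participants with high baseline IL-8 took them to 0.81 at week 24 (log baseline SD 1, correlation of log baseline with tumour slope 0.4). The within-participant ratio is immune to this.

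**Step 4: a different model.** Give each participant a constant ratio, a median time on study of 2.5 to 4 months, and an exit hazard ratio of exp(0.3) to exp(0.7) per SD of log2 ratio. The spurious fall at Day 336 then runs from 16% to 69% as that SD goes from 0.5 to 1.5. This width is why no single figure can be quoted.

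**Step 5: does a mixed model help?** With a true ratio near 0.25 and scan-based exit, the raw week-48 mean was 0.15 (ρ = 0.3) and 0.07 (ρ = 0.6). A random-slope model on log IL-8 gave 0.23 and 0.19. The bias shrinks but does not vanish.

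**The case against.** The strongest reply is that the coupling is borrowed. Section 5.4.2 describes patients on checkpoint inhibitors without IL-8 blockade. Here the antibody suppresses free serum IL-8 directly (Section 5.5.2), and it may break the link. That stands: the effect is conditional, and at zero coupling the ratio does not move.

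Several other points also stand in part:

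- Progression samples and treatment beyond progression reduce or delay the loss, though in the check they did not remove it.
- Loss through scheduled scans cannot act before about week 8. Section 8.1 allows earlier exit for toxicity or clinical deterioration, but nothing in the documents sizes it.
- The detailed biomarker schedule in Section 9.8 is redacted, so late IL-8 sampling cannot be confirmed. The SAP may also contain handling that is not visible here.

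A reader might infer two stronger things. One is that loss of progressors must by itself generate a falling curve of a known size. The documents support neither the necessity nor a number. The other is that the recommended Phase 2 dose rests on such a curve. Section 5.5.2 says that the dose was selected on the totality of Part 1 data. Its argument for the 2-weekly option uses Cycle 2 Day 1 values from the first 3 participants, which showed a rise and precede any scheduled scan. No dose decision is shown to depend on a late by-day mean.

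**Conclusion.** The point holds as a conditional weakness in a descriptive secondary analysis. If IL-8 change on the antibody remains correlated with tumour change, the planned by-day ratio can show or exaggerate a late fall and can distort later cohort contrasts. Across the assumed inputs of Steps 2 and 3, a true ratio of 1.00 would read about 0.58 to 0.83 at week 24. With no correlation it would read 1.00. These figures rest on assumed slopes, variances, correlations and exit rules, and none can be checked against the documents. Visits before the first scan should be little affected. This is a worthwhile improvement to how IL-8 durability is reported, and it leaves the trial's primary conclusions untouched.

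**What to change.** - **Cohort comparisons.** Base them on one nominal study day before the first scan, matched by day and not by cycle label. Cycle 2 Day 1 is Day 29 with the 28-day cycles of Parts 1A and 1B (Tables 2-3 and 2-4), but Day 43 with the 42-day first cycle of Part 1C (Table 2-6). Where IL-8 is sampled then, about Day 29 serves all: Cycle 2 Day 1 in Parts 1A/1B and Cycle 1 Day 29 in Part 1C.
- **Later days.** Keep the planned by-day summary. Add a repeated-measures mixed model on log IL-8 with cohort, day, cohort by day and log baseline, pooled or simplified where cohorts are small. Include samples taken at progression.
- **Display.** Print the number contributing under every plotted point.

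The cost is some SAP wording and one standard model, with no new data. The model assumes missing at random, so it reduces the bias but may not remove it.
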